15.5.1 Analysis of the primary efficacy variable

The primary efficacy analysis will be the comparison of the change from Baseline in ASDAS at Week 12 in the bimekizumab treatment group versus the CZP treatment group. Summary statistics will be presented by treatment group for ASDAS at each time point together with the changes from Baseline.

The statistical analysis of the primary efficacy variable will be conducted following a Bayesian paradigm. An informative prior will be used for the model intercept coefficient which in the primary model is equal to the mean change from Baseline in ASDAS in the CZP group when centered Baseline is observed at its mean of zero ($\beta_{CZP} \sim \text{Normal} [-1.78, \text{var}=0.0605]$). Vague priors will be used for all other model coefficients. All priors will be fully documented in the SAP and in the interim analysis SAP.

The Bayesian analysis will employ a linear regression model including treatment group and Baseline ASDAS (mean centered).

The posterior distributions of the mean changes from Baseline in ASDAS in the CZP and bimekizumab groups and of the difference in mean changes from Baseline between the treatment

groups (CZP - bimekizumab) will be summarized with means, standard deviations, 95% credible intervals and 95% Highest Posterior Density intervals. The posterior probability that the difference between treatment groups in the mean change from Baseline in ASDAS is greater than zero will also be presented. The posterior probability that bimekizumab achieves a lower ASDAS score at Week 12 compared to CZP will be derived from this distribution.

The study will be considered a success if the posterior probability of the difference in the mean change from Baseline in ASDAS between the CZP and bimekizumab treatment groups (CZP - bimekizumab) being greater than zero is at least 97.5% (ie, the lower bound of the 95% credible interval of the difference between treatment groups in the mean change from Baseline in ASDAS is zero or greater).

If further information (independent to this study) regarding the CZP treatment group response comes to light subsequent to writing this protocol then this prior may be updated prior to study unblinding, and details of this will be supplied in the SAP and the CSR. Note that the prior will not be updated based upon accrued study data at any time point.

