## 2.4 Determination of sample size

A sufficient number of subjects will be enrolled to ensure that at least 60 subjects are available in the main study at Week 12 to compare the change from Baseline in ASDAS between BKZ and CZP. This will also provide at least 25 subjects enrolled in the PET-CT or PET-MRI substudy from multiple sites. Subjects will be randomized in a 2:1 ratio to receive BKZ or CZP respectively.

The sample size was calculated to provide at least 80% power to detect a difference between treatment groups in the mean change from Baseline in ASDAS at Week 12 of 0.89 (group mean change from Baseline for CZP and BKZ being -1.78 and -2.67 respectively) with a common standard deviation (SD) of 1.17 using frequentist methods for the comparison of the treatment group mean change from Baseline in ASDAS at Week 12 with Baseline ASDAS as a covariate (Overall and Starbuck, 1979).

The correlation between Baseline and Week 12 raw ASDAS was assumed to be 0.35. Note that the informative prior for the model intercept to be used in the Bayesian modelling of the primary efficacy variable, given by  $\beta_{CZP} \sim \text{Normal}(-1.78, \text{var}=0.0605)$ , contributes an effective sample size of approximately 20 CZP subjects. Prior data conflict will be investigated, and a vague prior will be used for the model intercept coefficient if prior data conflict is evident.

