Note that a clarification regarding the sample size for this study was provided in protocol amendment 3. As indicated above, the planned sample size of at least 60 subjects provides sufficient power to detect meaningful treatment differences in the primary efficacy variable whilst also providing at least 25 subjects for the PET-MRI or PET-CT substudy. However, due to complexities in the initiation of sites capable of performing PET-MRI or PET-CT scans, more than the planned 35 non-PET-MRI/CT substudy subjects were screened and randomized before it was possible to close enrolment at the sites not participating in the substudy. Owing to the novelty of the PET-MRI/CT outcomes within this disease area, it is considered important to ensure at least 25 evaluable subjects are included in the assessment of this exploratory objective to maximize the possibility of identifying the salient factors or variables that might differ between the treatment groups and, therefore, the total sample size is increased to at least 72 subjects. This sample size increase will not negatively impact the power to detect a difference in the primary efficacy variable at Week 12 (ie, it will remain >80%), but will ensure that the target number of subjects are included in the exploratory analysis of changes in bone formation at Week 12 and Week 48. Since the analyses of PET-MRI/CT data are exploratory and treatment effect sizes are unknown, formal power calculations were not performed. Clinical expertise does, however, indicate that a sample size of at least 25 subjects in the substudy will characterize broad differences between treatment groups.

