### 8.1.2.1 Bayesian modeling

The primary statistical analysis of the primary efficacy variable at Week 12 will be conducted following a Bayesian paradigm. The Bayesian analysis will be performed using a linear regression model including treatment group and Baseline ASDAS (mean centered using the overall ASDAS mean). The model will be parameterized such that the effect of CZP is represented by the intercept parameter whilst the effect of BKZ is additive to this. An informative prior will be used for the model for the intercept coefficient which, in the primary model, is equal to the mean change from Baseline in ASDAS in the CZP group when the centered Baseline mean is zero ( $\beta_{CZP} \sim \text{Normal} [-1.78, \text{var}=0.0605]$ ). Vague priors will be used for the other model coefficients, ie, centered Baseline coefficient and additive effect of BKZ.

Proof of Concept (PoC) will be declared if the posterior probability of a positive difference in the mean change from Baseline in ASDAS at Week 12 between the CZP and BKZ treatment groups (CZP-BKZ) is 0.975 or greater (ie, the lower bound of the 95% credible interval of the difference between treatment groups in the mean change from Baseline in ASDAS is zero or greater).

The model to be used is as follows:

$$y_i \sim \beta_{CZP} + \beta_{bl}x_{i,bl} + \beta_{BKZ}x_{i,BKZ}$$

Where  $i$  indexes the  $i = 1, \dots, N$  subjects,  $y_i$  is the change from Baseline in ASDAS at Week 12 for subject  $i$ ,  $x_{i,bl}$  is the centered Baseline ASDAS for subject  $i$ ,  $x_{i,BKZ}$  is a variable equal to 1 if subject  $i$  was randomized to the BKZ group and 0 if not,  $\beta_{CZP}$  is the model intercept,  $\beta_{bl}$  is the coefficient for the centered Baseline ASDAS, and  $\beta_{BKZ}$  is the additive effect of BKZ in addition to the effect of CZP.

The prior distributions for the model parameters are:

$$\begin{aligned}\beta_{CZP} &\sim N(-1.78, \sigma_{CZP}^2 = 0.0605) \\ \beta_{bl} &\sim N(0, \sigma_{bl}^2 = 10^6) \\ \beta_{BKZ} &\sim N(0, \sigma_{BKZ}^2 = 10^6)\end{aligned}$$

where the prior for  $\beta_{CZP}$  is worth approximately 20 subjects (Section 2.4). The sample sizing for this study was based on the assumption that  $\sigma^2=1.1$  which was based on the CZP data available from a single internal study (Section 8.1.2.2).

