### 8.1.2.2 Building the prior

The CZP prior for this study has been built based on UCB study AS0001.

Study AS0001 was a Phase 3, multicenter, randomized, double-blind, placebo-controlled study to evaluate the efficacy and safety of 2 dose regimens of CZP in subjects with active axial spondyloArthritis (axial SpA). Subjects were randomized in a 1:1:1 ratio to receive one of three treatment regimens:

- CZP administered subcutaneously (sc) at the dose of CZP 400mg every 2 weeks (Q2W) at Weeks 0, 2, and 4 followed by CZP 200mg Q2W sc;
- CZP administered sc at the dose of CZP 400mg Q2W at Weeks 0, 2, and 4 followed by CZP 400mg every 4 weeks (Q4W) sc;
- Placebo.

In this study AS0001, one of the secondary efficacy variables was the change from Baseline in ASDAS; the primary efficacy variable for the current study AS0013.

To build the prior using these data, subjects in the CZP 400mg treatment group were removed since their CZP responses were sufficiently different from those of the CZP 200mg subjects (leaving 105 CZP 200mg subjects with Baseline and Week 12 data available), and the linear model detailed in [Section 8.1.2.1](#) was fitted to just the Placebo and CZP 200mg treatment groups with Placebo as the additive treatment effect (a treatment group by Baseline ASDAS interaction was also included in the model for this historical).

The estimated model was used to estimate the distribution  $\beta_{CZP} \sim N(-1.78, \sigma_{CZP}^2 = 0.0078)$  and might be used as a prior for the CZP mean response. However, in order to take into account expected study to study variation in the estimated CZP parameter  $\beta_{CZP}$ , this prior was discounted (the SD was inflated) to arrive at the prior given in [Section 8.1.2.1](#) (by inflating the SD by 2.788 to give an effective sample size of approximately 20 subjects).

The historical data in study AS0001 gave the opportunity to build an informative prior for the overall effect of Baseline ASDAS in the proposed study (ignoring treatment group since a Baseline by treatment group interaction is not expected). However, since the AS0001 study only included Placebo and CZP treatment group data there is currently no data available with which to confirm whether or not the estimated Baseline ASDAS coefficient of -0.66 for CZP is also similar for BKZ. Accordingly, whilst a Baseline by treatment group interaction in the proposed

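### The CZP prior appears to refer to AS0001's mean Baseline ASDAS but is applied at AS0013's own mean; aligning the two takes one constant

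*SAP*

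**What the plan says.** SAP 8.1.2.1 regresses the Week 12 change in ASDAS on treatment and "Baseline ASDAS (mean centered using the overall ASDAS mean". The intercept represents CZP and carries the only informative prior, N(-1.78, variance 0.0605). Proof of concept (PoC) requires a posterior probability of at least 0.975 that CZP - BKZ exceeds zero. Protocol 15.5.1 reads the intercept the same way, as the CZP mean change "when centered Baseline is observed at its mean of zero".

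SAP 8.1.2.2 explains where -1.78 comes from. The 8.1.2.1 model, with a treatment-by-Baseline interaction added, "was fitted to just the Placebo and CZP 200mg treatment groups with Placebo as the additive treatment effect" of AS0001 (105 CZP 200mg subjects). This gave N(-1.78, 0.0078). The SD was then multiplied by 2.788 "in order to take into account expected study to study variation in the estimated CZP parameter", leaving a prior worth about 20 subjects. The same section says no data yet show whether "the estimated Baseline ASDAS coefficient of -0.66 for CZP is also similar for BKZ", and so keeps a vague prior on the slope.

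SAP 2.4 adds a planning assumption: "The correlation between Baseline and Week 12 raw ASDAS was assumed to be 0.35". It plans at least 60 subjects at 2:1, and later "the total sample size is increased to at least 72 subjects".

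Neither document prints a centring value, AS0001's mean Baseline ASDAS, or an expected mean for AS0013.

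**The concern.** An intercept in a mean-centred model is the expected response at the mean of the data being fitted. Fitted to AS0001, the model gives the CZP change at AS0001's mean Baseline. In AS0013 the same number becomes the prior for the CZP change at AS0013's mean Baseline. These are the same quantity only if the two means agree, and nothing in the plan aligns them.

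That the means agree cannot be taken for granted. AS0001 is described as active axial spondyloarthritis. AS0013 enrols radiographic AS with hs-CRP above the upper limit of normal at Screening (Protocol 6.1), and CRP is a component of ASDAS.

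The quantity affected is the one that decides PoC. If AS0013 subjects start higher (D > 0), CZP subjects should improve by more than 1.78. The prior then holds the CZP estimate back, which favours bimekizumab. If they start lower (D < 0), a real bimekizumab advantage becomes easier to miss. The documents do not make either direction more likely.

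**Working it through.** **Inputs.** Prior N(-1.78, 0.0605) and CZP slope -0.66 (SAP 8.1.2.1, 8.1.2.2); SD 1.17, correlation 0.35 and difference 0.89 (SAP 2.4); 20 CZP/40 BKZ, or 24/48 at 72 subjects. D is an assumption and is varied.

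**The plan's own figures.**
- Prior variance: 0.0078 x 2.788² = 0.0606 (stated 0.0605).
- Residual SD: 1.17 x sqrt(1 - 0.35²) = 1.096. Effective size: 1.096²/0.0605 = 19.9; with SD 1.1, 1.21/0.0605 = 20.0 (stated about 20). The printed σ² = 1.1, taken as a variance, gives 18.2, so SD s = 1.1 is used below.
- Slope: with equal SDs, a correlation of 0.35 implies 0.35 - 1 = -0.65, close to -0.66.
- Location of the prior: 105 x 0.0078 = 0.82 is a plausible residual variance. That fits an intercept estimated at or near AS0001's mean; far from it, the variance would be larger.

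**Shift caused by D.** Weight of the prior on the CZP mean: w = (s²/nC)/(s²/nC + 0.0605).
- nC = 20: 0.0605/0.1210 = 0.50, so the shift in CZP - BKZ is 0.50 x 0.66 x D = 0.33 x D.
- nC = 24: 0.0504/0.1109 = 0.455, so the shift is 0.30 x D.

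Other readings of the residual variance give 0.24 to 0.35 x D.

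**Probability of PoC**, with known variance and the conflict switch ignored:
- Posterior variance = 1/(nC/s² + 1/0.0605) + s²/nB
- Sampling variance = (1 - w)² x s²/nC + s²/nB
- P = 1 - Φ[(1.96 x sqrt(posterior variance) - true difference - shift)/sqrt(sampling variance)]

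Example at 20/40, no true difference, D = +0.5: posterior variance 0.0605 and sampling variance 0.0454, so (0.482 - 0.165)/0.213 = 1.49 and P = 6.8%.

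| D | False PoC, 20/40 | False PoC, 24/48 |
|---|---|---|
| -0.5 | 0.1% | 0.1% |
| 0 | 1.2% | 1.2% |
| +0.2 | 2.5% | 2.6% |
| +0.4 | 5.0% | 5.0% |
| +0.5 | 6.8% | 6.7% |

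At a true difference of 0.89, P(PoC) is 97.2% (20/40) and 98.6% (24/48) at D = 0, and 87.3% and 92.6% at D = -0.5.

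**Scale for D.** The between-study SD implied by the discount is sqrt(0.0605 - 0.0078) = 0.23. Then 0.23/0.66 = 0.35, so D = 0.35 alone moves the CZP mean by one such SD. D = +1.0 (23.8%, 22.7%) is an upper bound: a shift of 0.66/0.246 = 2.7 prior SDs, at which the conflict check would often act.

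**Conflict check.** The SAP gives no threshold, so a two-sided prior-predictive check was assumed at 20/40. At D = +0.5, checks at the 5% and 20% levels leave false PoC at 6.6-6.9%. At D = +1.0 they trigger in 46% and 81% of trials, leaving 19.9% and 10.6%.

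**Simulation of the full regression** (residual variance integrated out, Baseline SD 1.17, 5,000 null trials per scenario). With own-mean centring, false PoC at D = 0 and +0.5 is 1.4% and 7.8% (20/40), and 1.2% and 6.7% (24/48). With AS0001-mean centring it is 1.3-1.9% and 1.3-1.8% for D from -1.0 to +1.0, and P(PoC) at 0.89 is 95-97% and 98-99%.

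**The case against.** The strongest reply is that the plan already allows for this. The prior SD was inflated for study-to-study variation, and a Baseline difference is one source of it. Averaged over the SAP's prior for the CZP mean, false PoC is 2.5% at both sample sizes. Even if all between-study variation came from Baseline, D > 0.40 would be 0.40/0.35 = 1.15 SDs, roughly a one-in-eight chance. The conflict check can drop the prior, and the vague-prior repeat (SAP 8.1.6.2) and ANCOVA (SAP 8.1.6.3) would show a result that leans on it. Protocol 2.3 also reports similar baseline burden in AS and non-radiographic disease in a CZP trial, though the documents do not say whether that trial is AS0001.

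This is a fair limit on how serious the point is, and it rules out calling it a demonstrated error. It does not remove the point. A discount is meant for differences nobody can calculate, and the sponsor can calculate this one. The conflict check changes little at moderate D. The supportive analyses do not decide PoC, and none keeps the CZP prior while aligning Baseline.

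A second reply is that re-centring relies on a slope pooled over both arms, two-thirds of it from BKZ. At 20/40 and |D| = 0.5, a BKZ slope of -0.40 gives a pooled slope of (20 x 0.66 + 40 x 0.40)/60 = 0.487 in size. The remaining shift is about 0.50 x (0.66 - 0.487) x 0.5 = 0.04, against 0.165 now. A BKZ slope of -0.90 gives a pooled 0.82 and again about 0.04.

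A third reply concerns timing. Interim analysis 1 shows primary efficacy results to sponsor personnel (SAP 4.5.2), and the documents do not say whether it has taken place. If it has, changing the primary model would be hard to defend.

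**Conclusion.** The concern holds as a weakness in specification that should be fixed, with medium confidence. A reader cannot tell from the SAP at what Baseline ASDAS the value -1.78 applies, and on the natural reading it is applied at a different point from the one where it was estimated.

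The size depends on an unknown D. It stays within 2.5% false PoC up to D of about +0.2 and reaches 5% at about +0.4; a negative D costs power instead. These figures assume an effective prior size of 20, residual SD 1.1 and an AS0013 slope of -0.66. With a slope of -0.40, false PoC at D = +0.5 would be 3.6% (20/40) or 3.7% (24/48). They are a range, not an estimate of what will happen in this trial.

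**What to change.** In SAP 8.1.2.1, centre Baseline ASDAS at the fixed AS0001 mean used to derive -1.78, and print that value there and in 8.1.2.2. Keep the prior N(-1.78, 0.0605) and the vague slope. For SAP 8.1.3, report group means at AS0013's mean by adding β_bl x (AS0013 mean - AS0001 mean); the treatment difference is unaffected by this step. Record the departure from Protocol 15.5.1 in SAP 3.9 and align the interim SAP.

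The constant comes from outside the trial, so this respects the protocol's rule that "the prior will not be updated based upon accrued study data at any time point". It should be adopted only before any unblinded results are seen. Otherwise leave the primary analysis alone and add the re-centred model to SAP 8.1.6.2 as a prespecified sensitivity analysis.

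The cost is one constant in the code, a few sentences and no new data. At 20/40 the 95% credible interval widens from 0.973 (D = 0) to 0.98 at |D| = 0.5 and 1.00 at |D| = 1.0. At 24/48 it goes from 0.91 to 0.91 and 0.93.

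Only the Baseline part is removed. Another unfavourable between-study shift of 0.23 would still give about 4% false PoC: (0.482 - 0.50 x 0.23)/0.213 = 1.72. A shift that happened to offset the Baseline part would be uncovered.

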6.5 Retesting/rescreening

In the event of an isolated laboratory value outside the laboratory's normal range, the evaluation may be repeated on 1 occasion during the Screening Period. If a value from the repeated test is within the screening-specified ranges, the subject maybe enrolled.

Subjects whose Screening Period expires may be rescreened following discussion with the Sponsor.

Subjects who withdraw from the study may be replaced, up to a maximum of 10 subjects.

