- Mean, SD, median and CIs will use 1 decimal place more (or 1 more significant figure, depending on the original data reporting format) than the original data
- Coefficient of variation will be reported as a percentage to 1 decimal place

- Minimum and maximum will be reported using the same number of decimal places as the original data
- If no subjects have data at a given time point, then only n=0 will be presented. If n<3, then only n, minimum and maximum will be presented. If n=3, then only n, median, minimum and maximum will be presented. The other descriptive statistics will be left blank.

When reporting individual values and descriptive statistics for PK concentration and hs-CRP data, the following rules will apply with regard to rounding and precision:

- Individual values will be reported to the same level of precision as received from the bioanalytical laboratory
- Descriptive statistics will be reported to the same level of precision as the individual data for the minimum and maximum, to 1 additional significant figure for the mean (arithmetic and geometric), median, Q1, Q3, SD, and to 2 additional significant figures for the 95% CI for the geometric mean
- The geoCV will be reported as a percentage to 1 decimal place

All statistical tests will be carried out 2-tailed at the 5% level of significance unless otherwise stated. The following rules will apply for the presentation of any results relating to inferential statistical analysis:

- P-values will be presented to 4 decimal places; p-values less than 0.0001 will be presented as “<0.0001” and p-values greater than 0.9999 will be presented as “>0.9999”
- Posterior probabilities associated with the Bayesian analyses will be presented as percentages to 1 decimal place
- Means, SDs, medians, 95% credible intervals and highest posterior density intervals obtained from the Bayesian analyses will be presented to 1 decimal place

All statistical output will be presented in statistical appendices where appropriate.

Time to response data (Section 8.3.2.2) will be analyzed for the Treatment Period and across the study (Treatment Period + Treatment Extension Period). All other data tabulations will be performed by treatment group, visit and time point (where applicable) and no separate analyses based on study period will be presented.

The treatment groups will be displayed as follows in the TFLs, where BKZ refers to bimekizumab and CZP refers to certolizumab pegol:

- BKZ
- CZP

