### **4.2 Handling of dropouts or missing data**

#### **4.2.1 Efficacy data**

##### **4.2.1.1 ASDAS derivation**

If 1 component for the ASDAS is missing at a given visit, and the visit prior to the visit with the missing component data is not the Baseline or Screening visit, the following will apply: the missing component will be imputed by carrying the last observation for the given component forward, and the ASDAS will be calculated accordingly.

If no value is available for that component before the missing visit, or if the visit prior to the visit with the missing component data is either the Baseline or Screening visit, then the next observation will be carried backwards, and the ASDAS will be calculated accordingly.

If an unscheduled or repeat visit with non-missing data for the given ASDAS component is available and this visit is closer to the scheduled visit where the component data is missing, then the component data from the unscheduled/repeat visit will be used in the derivation of the ASDAS score.

If more than one component for the ASDAS is missing, ASDAS will not be calculated and treated as missing.

Any measurements of hs-CRP that are below 2 mg/L will be imputed with a fixed value of 2 mg/L for the purpose of deriving the ASDAS.

The statistical analysis will be performed based on the resulting derived values of ASDAS.

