### 4.4 Handling of measurements obtained at the EW visit

Subjects withdrawing early from the study should undergo the same assessments scheduled for the Week 48 visit as soon as possible after withdrawal (as an EW visit) and then enter the SFU Period, completing study participation with the SFU Visit 20 weeks after their final dose of IMP.

The following rules will apply with regard to the inclusion of the results obtained at the EW visit in the descriptive summaries:

- Any measurements conducted at the EW visit should be included in the summaries for the respective scheduled visit, if the EW visit occurs at the time of the next scheduled visit. For example, if the EW visit occurs on Day 42, the results would be summarized together with the Visit 6 (Week 6, Day 42) results
- If the EW visit does not correspond to the day of a scheduled visit, the assessments of the EW visit should be mapped to the nearest scheduled visit, relative to the Baseline visit date, following the last scheduled visit where assessments are available
- If the date of the EW visit is equidistant between 2 scheduled visits at which no scheduled assessments were performed, the assessments from the EW visit will be mapped to the earliest of these visits
- If an EW visit mapping results in data being mapped to a visit where the specific assessment is not actually collected per the protocol schedule of assessments, these data will not be included in the summary statistics and will be listed only
- The only exception to the above rule is for ADA (for both BKZ and CZP) assessments, in which all early withdrawal visit assessments will be assigned to the next scheduled visit at which ADA are assessed. The rationale for this is that ADA positivity is summarized over a given study period. As part of that summary, a table indicating the first visit at which ADA positivity is observed will be presented. In order to match the number of subjects who were ADA positive at specific visits with the overall positivity for the period, it is necessary to ensure that ADA positivity is attributed to a visit where ADA antibody assessments were performed

Assessments from the EW visit will be displayed as the mapped visit and will be flagged in the by-visit data listings.

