In addition to the primary Bayesian analysis where subjects with missing data will be excluded from the analysis, a supportive analysis based on imputed or predicted values for the change from Baseline in ASDAS at Week 12 will be performed.

Predicted Week 12 values for the subjects who do not have ASDAS values for the Week 12 visit will be obtained from a Mixed Model Repeated Measures (MMRM) analysis. The model will include treatment group, visit and the treatment group by visit interaction as fixed effects (visit as a categorical variable) and Baseline ASDAS as a continuous covariate. Subject-level random intercepts and slopes (visit as a continuous variable) will be included in the model and a 2 x 2

unstructured covariance matrix for these random effects will be used, along with a simple covariance structure for the within-subject errors.

If the model fails to converge then the simpler subject-level model including the intercept as only random effect will be fitted. If there are still problems with convergence and/or if the estimated response covariance matrices (random effects and response) are not positive definite, then alternative models will be considered, eg, allowing the random effects covariance parameters to be unbounded, or modelling the response covariance structure without using random effects.

The combination of observed and predicted values of change from Baseline in ASDAS at Week 12 obtained from the MMRM will then be modelled as the response variable in this supportive Bayesian analysis.

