### **8.1.2.3 Prior data conflict**

Prior data conflict will be investigated for all informative priors through use of graphical displays. If there is evidence of prior data conflict for a given parameter, then a vague prior will be used for that parameter.

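### The supportive Bayesian analysis models predicted Week 12 ASDAS changes as if they had been observed, so its posterior SD is too small (supportive analysis only; low severity)

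*SAP*

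**What the plan says.** SAP 8.1.2.1 excludes subjects with missing data from the primary Bayesian analysis and adds a supportive one. A mixed model (treatment, visit, their interaction, Baseline ASDAS, subject-level random intercepts and slopes) supplies predicted Week 12 values where they are missing. Predictions and observations then serve together as the outcome: "combination of observed and predicted values of change from Baseline in ASDAS at Week 12 obtained from the MMRM will then be modelled".

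SAP 8.1.3 refers missing data to Section 4.2.1. For ASDAS that section deals with a single missing component ("the missing component will be imputed by carrying the last observation for the given component forward") and with low hs-CRP values, not with prediction error. SAP 4.4 adds that, for an early withdrawal, "the assessments of the EW visit should be mapped to the nearest scheduled visit" after the last one attended. SAP 8.1.6.1 repeats all supportive analyses on the FAS. SAP 3.1 fixes the display: "Posterior probabilities associated with the Bayesian analyses will be presented as percentages to 1 decimal place".

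On priors, the CZP mean has N(-1.78, variance 0.0605), obtained "by inflating the SD by 2.788 to give an effective sample size of approximately 20 subjects". SAP 8.1.2.3 adds: "If there is evidence of prior data conflict for a given parameter, then a vague prior will be used for that parameter". SAP 8.1.6.2 repeats the primary analysis under three alternatives: (1) all priors vague; (2) N(-0.66, variance 25) for the Baseline slope, called informative, with the informative CZP prior; (3) the same slope prior with a vague CZP prior.

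**The concern.** A model prediction has less scatter than a real observation. If predictions enter the regression as data, the residual variance falls while the sample size counts every subject in full. Both effects shrink the posterior SD.

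The SAP describes no residual draw, no parameter draw, no multiple imputation and no joint model for the missing values. It does not use the word single, but one prediction per subject, treated as observed, is the plain reading.

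This run yields the only posterior probability in the plan that includes subjects without Week 12 data. A reader would use it to judge whether the primary result is robust to dropout, and would see added certainty that is partly an artefact.

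**Working it through.** **Inputs.** SAP 2.4: difference 0.89, SD 1.17, Baseline to Week 12 correlation 0.35, at least 60 subjects, 2:1. SAP 8.1.2.1: CZP prior variance 0.0605. Protocol 6.5: "Subjects who withdraw from the study may be replaced, up to a maximum of 10 subjects". The plan gives no missing rate. Rates of 5%, 10%, 14% (10/72 = 13.9%, an anchor only) and 20% are assumed.

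**The plan's own figures.**
- Residual SD = 1.17 x sqrt(1 - 0.35^2) = 1.096; variance 1.2012.
- Power, 20 v 40: SE = 1.096 x sqrt(1/20 + 1/40) = 0.300; 0.89/0.300 = 2.965; Phi(2.965 - 1.96) = 84.3%. The stated 80% or more is reproduced.
- CZP prior: 0.0078 x 2.788^2 = 0.0606; effective sample size 1.2012/0.0605 = 19.9. Reproduced.
- In SAP 8.1.2.1, "The sample sizing for this study was based on the assumption that" the residual variance is 1.1. That value matches the inputs as an SD, so 1.2012 is used as the variance here.

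**Formula for the posterior SD of the difference.** With the planned CZP prior, ignoring the small contribution of the Baseline slope:

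SD = sqrt[ s2/n_BKZ + 1/(n_CZP/s2 + 1/0.0605) ]

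If all 60 subjects were observed: sqrt[1.2012/40 + 1/(20/1.2012 + 16.53)] = sqrt[0.03003 + 0.03014] = 0.245.

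**Simulated trials, N = 60.** No true difference; ASDAS at Weeks 4, 8 and 12; missing completely at random; CZP prior centred on the truth; 1,500 trials per setting. The comparator is multiple imputation (20 draws). Results when random effects give 0.6 of the Week 12 variance:

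| Missing | s2 with predictions as data | SD by formula | Simulated SD | Multiple-imputation SD | Ratio |
|---|---|---|---|---|---|
| 5% | 1.159 | 0.242 | 0.2423 | 0.2491 | 0.973 |
| 10% | 1.114 | 0.238 | 0.2387 | 0.2524 | 0.946 |
| 20% | 1.035 | 0.232 | 0.2322 | 0.2614 | 0.888 |

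The planned SD falls below the 0.245 that complete data would give, and keeps falling as more data are lost. With random-effect shares of 0.4 to 0.8 the ratio is 0.966-0.983, 0.931-0.965 and 0.859-0.927, so the SD is 2-3%, 4-7% and 7-14% too small.

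**Simulated trials, N = 72.** Adjacent-visit correlation 0.6, planned CZP prior. One set (4,000 trials) gave a shortfall of 3.2%, 6.3% and 8.9% at 5%, 10% and 14% missing. A second gave about 3%, 5%, 7% and 10% at 5%, 10%, 14% and 20%.

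**Effect on the printed probability, point estimate fixed.** A correct 97.0% has z = 1.881. The reading without prediction error is Phi(1.881/ratio):
- 5%: 1.881/0.973 gives 97.3%; 1.881/0.968 gives 97.4%.
- 10%: 1.881/0.95 gives 97.6%; 1.881/0.937 gives 97.8%.
- 14%: 1.881/0.93 gives 97.8%; 1.881/0.911 gives 98.1%.

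**False success (97.5% rule met with no true difference), planned prior centred on the truth, N = 72, correlations 0.4 to 0.8.** 1.6-1.9%, 1.3-2.5%, 1.7-3.0% and 2.5-4.0% at 5%, 10%, 14% and 20% missing. Monte Carlo error is about 0.5 points (1.96 x sqrt(0.025 x 0.975/4000)).

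**Secondary point: weight of the Baseline prior.** Slope SE = 1.1/(Baseline SD x sqrt(N - 1)), with Baseline SD assumed 0.6 to 1.17:
- SD 1.17, N = 72: SE 0.112; weight 0.0125/25.01 = 0.05%.
- SD 0.6, N = 60: SE 0.239; weight 0.0570/25.06 = 0.23%.

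Alternative 2 therefore repeats the primary run and alternative 3 repeats alternative 1. Alternative 1 still tests the CZP prior.

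**The case against.** The strongest case against is that nothing is decided on this run. Proof of concept rests on the complete-case primary model, and the repeated-measures models in SAP 8.1.6.4 and 8.1.6.5 already handle missing visits with valid standard errors. This stands and is why the severity is low. Those models use no CZP prior and give no posterior probability, so they do not replace this run.

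Few values may need prediction. Component carry-forward fills some gaps, early-withdrawal mapping may fill others (although SAP 4.4 states it for descriptive summaries), and missing data is a protocol-deviation category that can remove subjects from the PPS. This also stands for the PPS; the FAS repeat could contain more predicted values.

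The 97.0% example sits next to the threshold. At the design effect with complete data, 0.89/0.245 = 3.63, which prints as 100.0% with or without the fault. Credible limits, shown to 1 decimal, would mostly not change at low missing rates. Both are fair: the artefact matters only for a borderline result.

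Three stronger readings are tempting:
- That false success is generally inflated. With the planned prior centred on the truth it clearly exceeds 2.5% only at about 20% missing.
- That the SD is as much as 10-20% too small at 20% missing. Those are vague-prior figures. SAP 8.1.6.2 applies vague priors to the primary analysis, not to this run, so they would apply only if prior-data conflict made the CZP prior vague.
- That the Baseline prior distorts the results. It does almost nothing, which is the complaint. SAP 8.1.2.2 also explains the caution: no data confirm the -0.66 slope for BKZ.

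**Conclusion.** The point holds for the supportive analysis as written. With the planned CZP prior the posterior SD is too small by about 2-3%, 4-7%, 7-9% (correlation 0.6) and 7-14% at 5%, 10%, 14% and 20% missing. The direction was the same in every setting; the size depends on a missing rate that the plan does not give. The replacement cap is not a missing rate, and neither is the gap between 60 subjects at Week 12 and 72 in total, because the increase to 72 was made for the PET substudy.

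The multiple-imputation comparator did not carry uncertainty in the variance components, so the shortfall is, if anything, slightly understated.

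A reader might infer that the primary result or the success rule is compromised. The documents do not support this, because the primary model excludes subjects with missing data and uses no predicted values.

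The secondary point also holds: two of the three prior alternatives add no information, unless prior-data conflict has already made the primary CZP prior vague. Overall severity is low.

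**What to change.** **Supportive analysis (SAP 8.1.2.1).** Replace the plug-in step by one of the following, and state which:
- treat missing Week 12 changes as unknowns drawn from their predictive distribution within the Bayesian fit. The fit must include the earlier visits; drawing from the treatment-plus-Baseline regression alone would only return the complete-case result;
- or use multiple imputation from the mixed model, drawing both the parameters and the residual, fit the 8.1.2.1 regression to each data set and combine the posterior draws.

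Report the number of imputed subjects by arm for the PPS and the FAS.

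**Prior alternatives (SAP 8.1.6.2).** Either call the Baseline prior vague and drop alternatives 2 and 3, or set its variance from the AS0001 standard error of the -0.66 slope, with a discount justified for the slope. The 2.788 factor was chosen for the CZP mean and does not transfer automatically.

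**Cost.** A few SAP sentences and minor programming; SAP 8.1.3 already plans posterior sampling with multiple chains. The supportive interval becomes slightly wider. Design, data collection and the primary analysis do not change.
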